9.1 Health Economic Analysis Plan

Interventions being compared: See (1) and (2) above.

Cost perspective: public sector, including local and central government costs falling on the NHS, social care, education, criminal justice and taxes and benefits.

Effectiveness measure: the primary measure will be wellbeing adjusted life years (WELLBYs) as defined by the UK Treasury – i.e. a one-point improvement in life satisfaction for one year¹⁸ – with quality adjusted life years (QALYs) as a secondary measure

Type of analysis: cost-effectiveness analysis for the local evaluation (1) and distributional cost-effectiveness analysis for the national evaluation (2).

Reported outcomes: model (1): incremental cost-effectiveness ratio and, for model (2), the reduction in lifetime inequality in health and wellbeing between babies born into the richest and poorest fifths of households in England. We will also report various policy-relevant secondary outcomes, including payback period and total discounted lifetime cost savings and benefits in terms of WELLBYs, QALYs and other policy-relevant outcomes (e.g. numbers of people achieving good General Certificate of Secondary Education (GCSE) results, lifetime income and poverty, employment, and crime outcomes). All outcomes derived from LifeSim will be interpreted as the long-term effects of referral, relative to non-referral, of parents to a co-located money advice service during the child's infancy, and will provide greater understanding of whether the intervention supports children's ability to achieve their fullest potential over the lifecourse.

Time horizon: Lifetime of the newborn babies.

Discounting: All costs and outcomes will be discounted at an annual rate of 3.5%, with sensitivity analysis using a 1.5% discount rate for health and wellbeing outcomes in line with HM Treasury "Green Book" guidance on economic appraisal in central government.

Statistical methods: Extrapolation of short-term trial outcomes (PHQ-8, GAD-7, household income) across the lifecourse using microsimulation, based on two linked LifeSim models: (1) LifeSim Childhood from 0 to 17, and (2) LifeSim Adulthood from 17 to the rest of life.

Sensitivity analyses: Probabilistic sensitivity analysis together with additional scenario analysis to handle structural uncertainties. These include the potential for "generational changes" in our data (e.g. the possibility that some of our model parameter estimates based on data from "Generation Z" born in 2000 may differ from those for babies born into "Generation A" in the 2020s).

9.2 Within-trial cost-effectiveness

This will be a long-term model-based evaluation.

9.3 Health economic modelling

RQ1. Figure 2 provides an overview of how WP1 links to WP2. Key trial outcomes that will inform long-term health, economic, social, and wellbeing outcomes for children include effects on parental depression (PHQ-8), parental anxiety (GAD-7) and household income. Given the following measures are based on similar concepts of anxiety and depression, we

will develop a mapping algorithm between the PHQ-8, GAD-7 and the Parental Malaise 9-item scale available through the Millennium Cohort Study (MCS) data and LifeSim.

Figure 2.

[figure not shown]

Figure 2. HWFinEL modelling approach

LifeSim will then be used to produce modelled individual-level simulated estimates of the long-term consequences for children of improvements in family income and parental mental health in infancy, including outcomes up to age 17 using the LifeSim Childhood module and outcomes for the rest of life using the LifeSim Adulthood module.

RQ2. To determine the long-term cost-effectiveness of a co-located WBA in LBTH, relative to no co-located WBA.

LifeSim will be used to extrapolate the long-term benefits for children, and related long-term cost savings to the public purse, of improvements in family income and parental mental health in infancy.

To harmonise the household income effects measured in the trial with the household income outcomes used in LifeSim, we will inflate year 2000 incomes using the standard gross domestic product (GDP) deflator used in UK central government economic appraisal. In further robustness checks we will harmonise our income variables using proportional changes and relative measures of income including income decile groups and the relative poverty line in both years (60% of median household income) to enable estimation of the consequences of shifting people from one decile group to another, and in and out of relative poverty.

Analysis will predict the long-term causal effects of changing family income alone, and parental mental health alone, and changing both outcomes together. To account for the potential reciprocal and mediating relationships between parental mental health and

household income, where improving household income may improve parental mental health, and vice versa, we will also conduct a mediation analysis using the first three sweeps of MCS data (at ages 0, 3 and 5). This will help us avoid double counting of long term benefits and clarify the direct effects of improvements in household income on parental mental health.

Long-term public costs are already programmed into LifeSim¹⁷ and entail public costs across four sectors: National Health Service (NHS) England, social care, education, and criminal justice. Short-term costs entail those related to the intervention (referral) and comparator (no referral). These will be ascertained using data collected during the trial on the type and number of advice service appointments attended, the average length of appointment and known advice staff costs. We will also record the cost of organising the appointment, which will comprise the time spent making the appointment and the cost of this time in the health visitor enrolment service. We will also liaise with local authority finance officers to discuss the costs of organising and delivering the WBA service, compared with conventional services, to ensure we are not missing any important delivery costs.

RQ3. Baseline demographic and economic characteristics of the trial intervention and control groups (e.g., household income, ethnicity, index of multiple deprivation (IMD) area-based quintile groups), will be used to make suitable assumptions about how short-term effects might generalise from the trial population to different segments of the general population of England with similar economic characteristics and capacity to benefit from WBA services. Our assumptions will be based primarily on rapid literature review and feedback from experts in welfare policy and the tax-benefit system in England, and secondarily on sub-group analysis by income and IMD within the trial sample (section 8.3.4). Outcomes will inform the reduction in lifetime inequality in health and wellbeing between babies born into the richest and poorest fifths of households in England.

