1.1 Rationale

Addressing the financial challenges faced by low and middle-income parents, especially during the crucial early years of child development, is vital for improving health outcomes for both parents and child (Pickett and Wilkinson 2015)³.

Almost two thirds of low and middle income parents with young children in East London's Tower Hamlets (LBTH), were worried about job security in 2021 and over half were financially insecure⁴. In neighbouring Newham (LBN), more than 50% of children live in poverty⁵ and 1 in 11 families live in temporary accommodation.

Evidence on improving access to financial advice services is promising (Reece et al 2021)⁶. By making these resources more accessible, parents can be empowered to navigate complex systems, and claim benefits they may be unaware of such as Universal Credit. This not only has the potential to enhance their financial stability but also to alleviate some of the mental health burdens associated with financial stress.

A previous review of the landscape of advice services located in health settings suggests there is strong support from health services because clinicians frequently encounter unaddressed social welfare needs which they are ill-equipped to address.

Integrating welfare benefit advice with HV appointments for the 6-8 week check-up is a promising approach. This critical period in a child's life is often marked by significant adjustments for new parents, and addressing financial concerns alongside health check-ups can have several advantages:

1. **Timely Support:** Parents are already engaged with health services, making it an ideal time to address any financial worries or unmet welfare needs.
2. **Holistic Care:** By integrating financial advice with health assessments, you can provide a more comprehensive support system that addresses both physical and financial health, recognizing the interconnectedness of these factors.
3. **Increased Access:** Co-location can help reduce barriers to accessing financial advice, especially for parents who may feel overwhelmed or unsure about seeking help separately.
4. **Immediate Referrals:** Health visitors can identify families in need of assistance during appointments and facilitate immediate referrals to financial advisors, streamlining the process.
5. NHS health visitors is a trusted service, take up of financial advice will benefit from nomination by trusted professionals.

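### Section 9.1 counts taxes and benefits as a public cost, but the cost list in 9.3 has no line for them, so costing by 9.3 would leave out the welfare payments the advice generates

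*Protocol*

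**What the plan says.** Protocol 9.1 fixes the perspective for the economic evaluation: "public sector, including local and central government costs falling on the NHS, social care, education, criminal justice and taxes and benefits". That makes five heads.

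Protocol 9.3, under RQ2, describes what is to be costed. The long-term costs already built into LifeSim "entail public costs across four sectors: National Health Service (NHS) England, social care, education, and criminal justice". Short-term costs are those of referral and of no referral, to be found from "the type and number of advice service appointments attended, the average length of appointment and known advice staff costs", together with "the cost of organising the appointment, which will comprise the time spent making the appointment". The team will also talk to local authority finance officers "to ensure we are not missing any important delivery costs".

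On the effect side, 9.3 names the trial results that feed the model: "effects on parental depression (PHQ-8), parental anxiety (GAD-7) and household income". LifeSim then extrapolates from income and parental mental health to long-term gains for the children and to savings for the public sector.

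Section 1.1 gives the route by which the advice is expected to work: parents can "claim benefits they may be unaware of such as Universal Credit". Sections 9.4 and 9.5 add no further cost item.

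**The concern.** Raising welfare income is a main mechanism of the service. On the perspective chosen in 9.1, each extra pound paid to a family is a public cost. On the list in 9.3 it is not charged anywhere, yet the same pound enters the model as household income and is credited with later gains and savings. The two sections therefore give different rules for the numerator of the ratio.

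What is at stake is the RQ2 ratio and the payback period and discounted cost savings promised in 9.1. RQ3 is touched too, because it asks whether national roll-out is cost-effective, although the headline outcome named for the national model is the reduction in lifetime inequality. The trial's primary analysis of PHQ-8 is unaffected.

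**Working it through.** **Cost heads side by side**

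| Head | Perspective (9.1) | Costed (9.3) |
|---|---|---|
| NHS | yes | yes, long term |
| Social care | yes | yes, long term |
| Education | yes | yes, long term |
| Criminal justice | yes | yes, long term |
| Taxes and benefits | yes | no line |
| Advice delivery and booking | within public sector | yes, short term |

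Five heads are declared and four appear in the long-term list. The short-term sources cover appointments, staff and booking time, and the completeness check is limited to delivery costs.

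**Direction for the omitted outlay.** The protocol states no cost, ratio or benefit gain, so there is no figure of its own to reproduce. Write, per family and between arms:

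- D = cost of delivering and organising the advice
- B = extra welfare payments
- S = public savings in the four sectors
- E = effect (WELLBYs or QALYs)

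On the 9.1 perspective, before any later tax or benefit offset, the ratio is (D + B − S)/E. Following 9.3 sets B = 0 and gives (D − S)/E. The difference is B/E, which is positive whenever B and E are.

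**Illustrative size.** From the protocol: two full-time advisers and up to 16 months of service (4.2), and 1,153 participants at 1:1, so about 577 in the intervention arm. Assumed: GBP 45,000 a year per adviser.

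- Adviser cost: 2 × 45,000 × 16/12 = GBP 120,000.
- Per intervention participant: 120,000/577 = GBP 208.
- Assumed extra payments of GBP 250, 500, 1,000 and 2,000 per family per year, divided by 208, give 1.2, 2.4, 4.8 and 9.6.

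The base here is adviser salary only. Booking time and other delivery costs, which 9.3 does count, would lower these multiples.

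Effect on the ratio, with assumed D = 200, S = 100 and E = 0.05:

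- Following 9.3: (200 − 100)/0.05 = 2,000.
- With B = 250: (200 + 250 − 100)/0.05 = 7,000.
- With B = 1,000: (200 + 1,000 − 100)/0.05 = 22,000.

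**How large an offset would cancel it.** Discounting at 3.5% a year (9.1), GBP 1 a year from the child's age 20 to 64 has a present value of Σ 1.035^(−t), t = 20 to 64, = 11.70. Cancelling a one-off GBP 1,000 of extra payments therefore needs 1,000/11.70 = about GBP 85 a year in net tax receipts or benefit savings over those 45 years. If the GBP 1,000 is paid in each of three years, its present value is 1,000 × (1 + 1/1.035 + 1/1.035²) = GBP 2,900, and the offset needed is 2,900/11.70 = about GBP 248 a year. The 1.5% rate in 9.1 is a sensitivity analysis for health and wellbeing outcomes, so it is not applied to these money flows.

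**The case against.** The strongest reply is that 9.1 governs. It names taxes and benefits expressly, and nothing in 9.3 withdraws them. The four-sector sentence describes what LifeSim already contains and does not say that nothing else will enter the ratio. This stands in part: the omission follows only if 9.3 is taken as the full list. But the short-term data sources are also confined to delivery and booking, so if 9.1 governs, 9.3 is incomplete and the two still need reconciling.

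A reader might infer that the ratio is certain to be biased in favour of the service. The documents do not support that. Besides the condition just stated, the missing head covers taxes as well as benefits. The horizon is the babies' lifetime, and employment, lifetime income and poverty are among the reported outcomes, so later receipts or savings could run the other way. The protocol does not fix the net amount.

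Welfare payments are transfers and would net out from a societal viewpoint. That is a sound reason to show a scenario without them, but 9.1 chose a public-sector viewpoint and listed them as a cost.

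A reader might also infer that the data already planned will supply the missing figure. They may not. Table 2 lists only self-reported household income, with no breakdown by source. The benefits-claimed item in the process evaluation table comes from the advisers' administrative data, with no control-arm equivalent shown. Advice also covers employment, housing and debt, so an income difference is not all welfare payment.

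**Conclusion.** The contradiction stands: 9.1 declares a cost head for which 9.3 has no line. If costing follows 9.3, the extra welfare outlay is left out while its effects are credited, and the RQ2 ratio is lower by B/E than it would be with that outlay charged. The payback period and cost savings would be off the declared perspective in the same way.

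The contradiction and the B/E expression come from the text and algebra alone. The size does not: the salary, payment, saving and effect values are all assumptions. They show that the omitted item could equal or exceed adviser cost, not what it will be. The net effect after later tax and benefit flows is open. The matter should be settled before the economic analysis is run.

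**What to change.** Reconcile 9.1 and 9.3 as follows.

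1. Add to 9.3 a line for incremental tax and benefit flows, covering both extra payments and later receipts or savings.
2. Report the ratio on the 9.1 perspective, with a labelled scenario that excludes transfers.
3. State the data source: the between-arm difference in self-reported household income, supported by the advisers' records of benefits claimed.
4. State the assumed share of the income difference that is welfare payment, and vary it in the sensitivity analysis, because neither source gives that share in both arms.

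If follow-up is still open, the team could check whether the income item can separate welfare income, which would reduce reliance on step 4 but might need a questionnaire amendment.

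The cost is wording in 9.3 and in the health economic analysis plan, one added assumption, and probably a less favourable ratio.

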9.4 Sensitivity analyses

To estimate the general degree of uncertainty in cost-effectiveness estimates produced by LifeSim, we will conduct probabilistic sensitivity analysis based on empirical distributions around all the general causal effect parameters in LifeSim. To estimate the specific degree of uncertainty around key parameters of interest, such as a potential decline to the long-term sustained effect on maternal mental health, we will conduct scenario analysis using scenarios constructed in consultation with experts and informed by rapid literature review. We will also conduct scenario analysis around key assumptions about how the uptake of co-located money advice services varies among those with varying baseline economic circumstances (household income and IMD quintile group) and how the effect of uptake varies for those with varying levels of baseline economic circumstances (e.g. the richest fifth of households in England are less likely to be eligible for substantial unclaimed welfare benefits than the poorest fifth).

9.5 Additional considerations

If the trial does not meet the progression criteria (red traffic light), or referral to the co-located money advice service proves ineffective in improving short-term parental outcomes, LifeSim will be used to determine the minimum (threshold) level for which referral and uptake of the co-located money advice service is required to result in long-term cost-effectiveness. This

will inform the future design, implementation, and evaluation of co-located money advice service interventions.

10 Process Evaluation (embedded within WP1 trial)

Within the trial and WP1 will be an embedded process evaluation. The process evaluation will address key questions of implementation and delivery of the HWFinEL intervention.

This is an overview of the process evaluation. Process evaluation participant documentation, questionnaires, checklists and interview topic guides will be added as an amendment at a future date.

10.1 Theoretical framework

Theoretical frameworks from implementation science help clarify implementation questions, provide validated instruments to assess outcomes and barriers, and offer theory-driven explanations for success or failure. This evaluation will use the RE-AIM framework (Reach, Effectiveness, Adoption, Implementation, and Maintenance; Glasgow et al., 1999¹⁹), a widely used tool for translating research into practice and assessing public health impact. RE-AIM focuses on:

- **Reach:** the percentage of the target population that participates in a program
- **Effectiveness:** the positive and negative outcomes of the program
- **Adoption:** the percentage of settings and staff that participate
- **Implementation:** the extent to which the program is delivered as intended, including cost
- **Maintenance:** the sustainability of primary outcomes beyond six months.

We will explore the implementation of HWFinEL, through:

- 1) An implementation check list
- 2) Normalisation Process Theory (NPT; May et al., 2009²⁰) will be used. NPT helps understand the adoption, implementation, and maintenance of practices by focusing on four mechanisms:
 - **Coherence:** understanding the aims and logic of the intervention
 - **Cognitive participation:** building and sustaining a community of practice
 - **Collective action:** the operational work to embed the intervention
 - **Reflexive monitoring:** assessing and evaluating the intervention's impact.

Together, RE-AIM and NPT provide a comprehensive approach to evaluating and understanding implementation processes and outcomes.

10.2 Methods

10.2.1 Data Collection

- Anonymised data recording the number of parents eligible for the trial and those that take up the offer, collected at 6-8 week appointment with their health visitor.
- Qualitative interviews with 45 purposively selected participants, selected at random to represent diverse (ethnicity, gender, household structure) backgrounds and locations in the borough, will provide data on the experience of using the service and will inform the effectiveness of the service in the eyes of the users

- Approximately 20 council staff who deliver, have oversight of, or host the intervention will be asked to take part in telephone or face to face interviews at the mid-point of the trial (approximately 8 months after recruitment begins) towards the end of the intervention period. Interview questions will include: facilitators and barriers to set up and continuous monitoring, contextual factors affecting intervention delivery and sustainability.
- An implementation check list at 2 time points
- Researcher observations and fieldnotes during the set up and support phases of the intervention about what worked (or did not), for whom and in what circumstances to produce implementation themes.
- Notes of meetings of intervention oversight groups which document evolving decision making will be thematically organised. These notes will be continuously monitored during the set up and implementation phase to inform the internal pilot (see section 3.3.4). Findings will document how adaptations had to be made and why, what feedback mechanisms were in place and how they worked, what, if any, were unintended consequences, and what possible forward trajectories for the intervention²¹.

10.2.2 Analyses

- Our analytical approach will involve a structured and robust process of data collation, sorting, coding and thematic investigation against the evaluation questions (data analysis). An overview of the methods can be found in the table below.

Table 6: Process evaluation methods overview

REAIM domain	Data collection methods	Data collected	Data analysis methods
Reach	HVs appointment records All new mothers approached by HV	Anonymised data on Attendance, eligibility and interest in participation	Quantitative analysis
Reach	WBA administrative data	Attendances, benefits claimed	Quantitative analysis
Effectiveness	Trial	Participant questionnaires including financial gain and mental health outcomes	Quantitative analysis
Effectiveness	Parent interviews in person or virtual interview, recorded or notes taken	45 participants from intervention and control arms of the study. And 20 staff who deliver the intervention	Qualitative thematic analysis
Adoption/implementation/maintenance	interviews with intervention stakeholders	20 staff who deliver, have oversight of, or host the intervention	Qualitative thematic analysis
Adoption/implementation	Pre- implementation checklist	Minimum of 8 CFCs managers/ staff	
Adoption/implementation	Post- implementation checklist	Minimum of 8 CFCs managers/ staff	
Adoption/implementation/maintenance	In person observation, note taking	Minimum of 8 CFCs managers/ staff	Qualitative analysis of observation notes
Adoption/implementation/maintenance	Notes of meetings of intervention oversight groups	All new mothers approached by HV	Quantitative analysis

Qualitative data will be recorded, transcribed and analysed thematically. There are two main lines of enquiry for this data. The first (focussed on in the 45 participant interviews) is about the participant's experience of the service and its impact on their lives, augmenting the quantitative analysis, while the second (focussed on in the 20 interviews with delivery staff and 8 CFC managers/ staff) is about the organisational arrangements for delivery. An initial coding structure will be developed in advance, building on earlier work by the team (feasibility study, PPI consultations), and by Reece's study in Bradford, but this will be flexible to modification as themes emerge from the data. Coding will be undertaken by two researchers, with a sample cross checked by a second coder. NVivo or similar software will be used to facilitate the coding and analysis. Analyses of experience will focus on how and in what ways the advice has been taken up, impacts on household, and child activities and wellbeing, while analyses of organisational arrangements will focus on how and in what ways implementation was consistent across centres, what challenges were raised and how overcome, and how the implementation might best be adapted. Preliminary interpretations will be checked with the PPI group. Findings will be compared with those from the Glasgow model¹⁰, Beardon's work on HJP implementation⁹ and Reece⁷ to understand mechanisms of staff engagement, organisational arrangements and, indirectly, of families' health improvement.

